1.1 Study Schematic

Abbreviations: bpm = beats per minute; CRC = Cohort Review Committee; COVID-19 = coronavirus disease 2019 (severe acute respiratory syndrome coronavirus 2 [SARS-CoV-2]); IV = intravenous; R = randomization; RP2D = recommended Phase 2 dose; SOC = standard of care

- a. Patients will be evaluated for enrollment during the up to 7-day screening period. The complete list of entry criteria is provided in Section 4.0.
- b. A CRC will review blinded safety, tolerability, pharmacokinetic, pharmacodynamic, and disease measurement data, make decisions about escalating or de-escalating the bempegaldesleukin dose, and identify the RP2D (see Section 7.16).
- c. If the CRC determines additional patients may be randomized, 2 patients will be randomized (1 with bempegaldesleukin/SOC and 1 with placebo/SOC), treated with study drug, and observed for 72 hours. For every 2 patients, the Medical Monitor will review the blinded safety and tolerability data for the first 72 hours after study drug administration to determine if the next 2 patients may be randomized (Section 5.3).
- d. The Safety Follow-Up should occur 30 days (\pm 7 days) after discharge from the hospital or in-patient facility. See Section 5.7 for additional details.

Protocol No. 20-214-34

Note. The Safety Follow-Up should occur 30 days (\pm 7 days) after discharge from the hospital or in-patient facility. See Section 5.7 for additional details.

a. Earliest possible randomization day for the next eligible patients if approved by CRC (see Section 5.3).

b. Earliest possible randomization day for the next eligible patients if approved by Medical Monitor (see Section 5.3).

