3.0 STUDY OBJECTIVES

3.1 **Primary Objectives**

The primary objectives are:

- To evaluate the safety, tolerability, pharmacokinetics, and pharmacodynamics of bempegaldesleukin/SOC compared with placebo/SOC in patients with mild COVID-19.
- To evaluate the safety and tolerability of bempegaldesleukin administered as single IV dose and to define the RP2D of bempegaldesleukin in patients with mild COVID-19.
- To assess the effect of bempegaldesleukin on the time course and extent of changes in absolute lymphocyte counts.

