bempegaldesleukin/SOC and 1 with placebo/SOC) will serve as sentinel patients. Enrollment in each cohort will be staggered as presented in Figure 2 and Table 9. The Cohort Review Committee (CRC; see Section 7.16) will monitor blinded safety and tolerability data for the first 72 hours after study drug administration from the 2 sentinel patients before additional patients in that cohort are treated. If the CRC determines additional patients may be randomized, 2 patients will be randomized (1 with bempegaldesleukin/SOC and 1 with placebo/SOC), treated with study drug, and observed for 72 hours. For every 2 patients, the Medical Monitor will review the blinded safety and tolerability data from the first 72 hours after study drug administration to determine if the next 2 patients may be randomized (see Section 5.15). If it is not possible to assess the protocol-defined DLT criteria (see Section 5.3.2.1.1), the Medical Monitor will request a review of the safety data by the CRC. After 10 patients have completed a 7-day observation period for DLT (see Section 5.3.2.1 for additional details), the CRC will determine whether dose escalation or de-escalation from the tested bempegaldesleukin dose level can proceed. The CRC will document this decision that will be based on blinded data using predefined criteria, including the proportion of patients who experience a DLT (see Section 5.3.2). Patients who drop out of the study for reasons other than a DLT, before the DLT evaluation period (Days 1 to 7) has elapsed, may be replaced.

Table 9:	Staggered Dosing	Procedures for	Each Dose Cohort

Patient	Procedure
Patients 1 and 2	Randomize Patients 1 and 2.
	CRC reviews blinded safety and tolerability data for the first 72 hours after study drug administration to determine if Patients 3 and 4 can be randomized.
Patients 3 and 4	Randomize Patients 3 and 4 if CRC approves.
	Medical Monitor reviews blinded safety and tolerability data for the first 72 hours after study drug administration to determine if Patients 5 and 6 can be randomized. ^a
Patients 5 and 6	Randomize Patients 5 and 6 if Medical Monitor approves.
	Medical Monitor reviews blinded safety and tolerability data for the first 72 hours after study drug administration to determine if Patients 7 and 8 can be randomized. ^a
Patients 7 and 8	Randomize Patients 7 and 8 if Medical Monitor approves.

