- The RP2D of bempegaldesleukin based on the totality of the blinded, safety, tolerability, pharmacokinetic, pharmacodynamic, and disease measurement data. The RP2D may be determined based on the MTD dose or a dose lower than MTD. The RP2D may also be determined based on the immunologic effects of the study drugs, which could include effects on lymphocyte counts, cytokines, natural killer cells, T-cells, and other serum proteins and immune modulators. If it is not possible to assess the protocol-defined DLT criteria (see Section 5.3.2.1.1) for the entire cohort to determine dose escalation, the CRC may review unblinded data in accordance with Nektar Therapeutics internal procedures for unblinding.
- Whether dose levels other than those shown in Table 8 should be evaluated in consideration of the severity, duration, frequency of toxicities, pharmacokinetics, and/or pharmacodynamics observed at any dose.

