5.3.2.1.1 DLTs Related to Study Drug

AEs related to study drug(s) that will be defined as a DLT include the following:

- Any Grade \geq 3 drug-related AE.
- Any Grade ≥ 3 drug-related laboratory abnormality that is clinically significant per the Investigator.
- Respiratory compromise or other virus-related AE attributed to worsening COVID-19, such as severe hypoxia, cyanosis, or chest pain/pressure.

All AEs that meet DLT criteria must be recorded in the electronic data capture system within approximately 24 hours of awareness.

Each AE reported as related to study drug that meet any of the above definitions will be adjudicated by the CRC. If the event is confirmed to be at least possibly related to study drug, meets any of the above definitions, and is confirmed to have occurred in a patient treated with bempegaldesleukin, the event will be considered to be a DLT.

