Eligible patients will be enrolled into 1 of 3 dose cohorts with doses ranging from 0.00075 mg/kg to 0.003 mg/kg. The first two patients randomized and treated in each dose cohort (1 with bempegaldesleukin/SOC and 1 with placebo/SOC) will serve as sentinel patients. Enrollment in each cohort will be staggered as follows. A Cohort Review Committee (CRC) will monitor blinded safety and tolerability data for the first 72 hours after study drug administration from the 2 sentinel patients before additional patients in that cohort are treated. If the CRC determines additional patients may be randomized, 2 patients will be randomized (1 with bempegaldesleukin/SOC and 1 with placebo/SOC), treated with study drug, and observed for 72 hours. For every 2 patients, the Medical Monitor will review the blinded safety and tolerability data for the first 72 hours after study drug administration to determine if the next 2 patients may be randomized. If it is not possible to assess the protocol defined DLT criteria (see Protocol Section 5.3.2.1.1), the Medical Monitor will request a review of the safety data by the CRC. After 10 patients have completed a 7-day observation period for dose-limiting toxicity (DLT; see Protocol Section 5.3.2.1 for additional details), the CRC will assess the accumulated, blinded safety and tolerability data, as well as any available pharmacokinetic, pharmacodynamic, and disease measurement data, to determine whether dose escalation or de-escalation from the tested bempegaldesleukin dose level is warranted. This decision will be based on blinded data using pre-defined criteria, including the proportion of patients who experience a DLT (see Protocol Section 5.3.1). Patients who drop out of the study for reasons other than a DLT, before the DLT evaluation period (Days 1 to 7) has elapsed, may be replaced.

The RP2D of bempegaldesleukin in patients with mild COVID-19 will be based on the totality of safety, tolerability, pharmacokinetic, pharmacodynamic, and disease measurement data.

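### The recommended Phase 2 dose, a primary objective, is to be chosen from blinded data, so apart from the DLT count its evidence comes from cohorts that are half placebo

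*Protocol*

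**What the plan says.** Protocol 3.1 lists among the primary objectives "to define the RP2D of bempegaldesleukin in patients with mild COVID-19". Protocol 2.3 and 7.16 give that decision to the CRC.

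Protocol 5.3 states the data basis: "The RP2D of bempegaldesleukin based on the totality of the blinded, safety, tolerability, pharmacokinetic, pharmacodynamic, and disease measurement data". The word blinded is not isolated. Footnote b of the schematic in Protocol 1.1 says "A CRC will review blinded safety, tolerability, pharmacokinetic, pharmacodynamic, and disease measurement data" and then has the CRC identify the RP2D. Protocol 5.3 adds "The RP2D may also be determined based on the immunologic effects of the study drugs", naming lymphocyte counts, cytokines, natural killer cells and T-cells among them.

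The RP2D item has one unblinding clause. If DLT criteria cannot be assessed "for the entire cohort to determine dose escalation, the CRC may review unblinded data". Protocol 5.14 sets the same condition for cohort-level unblinding and gives its purpose as escalation or de-escalation. It does not mention the RP2D.

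For DLTs, Protocol 5.3 says of the escalation decision: "The CRC will document this decision that will be based on blinded data using predefined criteria, including the proportion of patients who experience a DLT". Under Protocol 5.3.2.1.1 an adjudicated event counts only if it "is confirmed to have occurred in a patient treated with bempegaldesleukin, the event will be considered to be a DLT". Protocol 5.3.1 counts CRC-confirmed DLTs among patients who received bempegaldesleukin and provides for unblinding where adjudication requires it.

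SAP 3.0 reads: "The RP2D of bempegaldesleukin in patients with mild COVID-19 will be based on the totality of safety, tolerability, pharmacokinetic, pharmacodynamic, and disease measurement data". SAP 12.0 declares no change from the protocol's analyses.

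**The concern.** Each cohort has 5 patients on bempegaldesleukin and 5 on placebo. If the CRC follows the stated rule, it compares dose levels on lymphocytes, cytokines, lower-grade adverse events and disease measures without knowing which patients had the drug. Two things are lost. The difference between dose levels is diluted. The CRC also has no control group with which to separate a drug effect from the natural course of lymphocytes in COVID-19, although Protocol 2.2.1 gives objective assessment as the reason for the placebo arm.

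The unblinding clause is least likely to apply where it would help most. Protocol 2.2.4 expects a low likelihood of toxicity at these doses. If DLTs are absent or easily classified, the condition for unblinding is not met, and the RP2D then rests mainly on the pharmacodynamic and other non-DLT data.

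**Working it through.** **The plan's own figure.** No alpha, power or effect size is stated. The only figure to reproduce is enrolment: 3 cohorts × 10 patients = 30, matching the approximately 30 in SAP 4.0.

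**Inputs.**
- Predicted median lymphocyte fold changes of 1.32, 1.49 and 1.77 at the three planned dose levels, from lowest to highest (Protocol 2.2.4.3). They are treated here as arm means.
- Allocation of 5 and 5 per cohort (Protocol 9.2), in successive pairs of one drug and one placebo patient (Protocol 5.15).
- Placebo fold change: not in the documents. Assumed 1.0, with a range of 0.9 to 1.2, and the same in every cohort.
- SD of the fold change within an arm: not in the documents. Assumed 0.4, with a range of 0.2 to 0.6, and the same in both arms and every cohort.

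**Dilution of the dose contrast.** Blinded cohort mean = (5 × drug + 5 × placebo)/10.

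| Placebo | Lowest dose | Middle dose | Highest dose | Highest minus lowest |
|---|---|---|---|---|
| 0.9 | 1.11 | 1.195 | 1.335 | 0.225 |
| 1.0 | 1.16 | 1.245 | 1.385 | 0.225 |
| 1.2 | 1.26 | 1.345 | 1.485 | 0.225 |

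Drug patients alone: 1.77 − 1.32 = 0.45. The mixed contrast is half of that whatever the common placebo value.

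**Precision.** By arm, the contrast compares two means of 5, so SE = √(2·SD²/5). Blinded, it compares two means of 10. Because the split is fixed at 5 and 5, the drug–placebo gap adds nothing to the sampling variance of a cohort mean, and SE = √(2·SD²/10).

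| Assumed SD | By arm: 0.45/SE | Blinded: 0.225/SE |
|---|---|---|
| 0.2 | 0.45/0.1265 = 3.56 | 0.225/0.0894 = 2.52 |
| 0.4 | 0.45/0.2530 = 1.78 | 0.225/0.1789 = 1.26 |
| 0.6 | 0.45/0.3795 = 1.19 | 0.225/0.2683 = 0.84 |

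The ratio is ½ × √2 = 0.71 at any SD, a loss of 29%. The larger cohort mean recovers part of the halving, but not all of it.

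**Adverse events not adjudicated as DLTs.** Suppose 2 of 10 patients in a blinded cohort have the same lower-grade event and events are unrelated to arm. The chance that k of them are on drug is C(5,k)·C(5,2−k)/C(10,2), which gives 10/45, 25/45 and 10/45 for k = 0, 1, 2, or 0.22, 0.56 and 0.22. Paired allocation gives the same result: 1/9 of the time both events fall in one pair (k = 1), otherwise the split is 0.25/0.5/0.25, so P(k = 1) = 1/9 + 8/9 × 0.5 = 0.56. The blinded 20% is therefore compatible with anything from 0% to 40% on drug.

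**Text.** No section links the RP2D to a by-arm review or to database lock. Protocol 9.6 and 9.7.1 mention lock and unblinding only as the deadline for changing analyses in the SAP.

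**The case against.** The strongest reply has four parts.

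1. The safety part is already handled. Treatment must be confirmed before an event counts as a DLT, and individual unblinding is also allowed for managing adverse events, expedited reporting and evaluation under the stopping rules (Protocol 5.14). This stands. A reader might infer that the DLT proportion or the MTD would be computed with the arms mixed, or that failure to assess DLT criteria is the only route to any unblinding. Protocol 5.3.1, 5.3.2.1.1 and 5.14 do not support either reading. The 0.22/0.56/0.22 split above does not describe the DLTs counted for the MTD.

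2. Nothing says that the CRC sees only pooled cohort means. It may see data by patient within known pairs, and drug concentrations would largely reveal who was treated. It is true that the actual dilution depends on how data are presented and on internal procedures that the documents do not give. But a review in which concentrations identify the arm is not the blinded review that the protocol describes. The protocol does not say how the blind is kept for these data.

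3. SAP 5.0 plans all tables by treatment with pooled placebo, and nothing requires the RP2D to be fixed before they exist. That is correct, but nothing ties the RP2D to those tables either, and the stated basis is blinded data.

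4. The study is descriptive and the RP2D is a committee judgement. This also stands: the loss in difference/SE illustrates lost information and is not a loss of power for a planned test.

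A reader might also compute a steeper loss by adding between-arm variance, as if patients were drawn at random from a 50:50 mixture. At SD 0.4 that would give 1.01 in place of 1.26. Fixed 5:5 allocation rules it out for the precision of cohort means.

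**Conclusion.** The point holds for the part of the RP2D decision that does not rest on DLTs. As written, the CRC chooses the RP2D from blinded data, and the cohort-level exception is optional, depends on DLT assessability and is aimed at escalation. Following the rule sets aside the randomised comparison for the immunologic effects, lower-grade events and disease measures that may decide the dose.

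On lymphocytes, the contrast between lowest and highest dose halves from 0.45 to 0.225 and difference/SE falls by a factor of 0.71. This assumes model medians stand in for means, a common placebo value, a common SD and a reader who sees only mixed cohort means. The absence of a control comparison does not depend on those assumptions as long as review stays blinded.

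A reader might infer that protocol and SAP contradict each other. The documents do not go that far: SAP 3.0 drops the word blinded but does not say that the choice uses unblinded data. It leaves the question open. The matter should be corrected. It does not show that the primary dose question would go unanswered.

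**What to change.** - Keep escalation review blinded as planned, with treatment confirmed for events adjudicated as DLTs.
- State that the RP2D is chosen after the last cohort's data are locked, from unblinded summaries by dose level against pooled placebo. Say who sees these summaries.
- Align the wording in Protocol 1.1 (footnote b), 2.3, 5.3 and 5.14 and in SAP 3.0.

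Choosing after lock also suits the CRC's make-up. It includes sponsor staff and at least one investigator (Protocol 7.16), and Protocol 5.14 otherwise keeps investigators and sponsor personnel involved in the study blinded.

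The cost is an edit to both documents and an RP2D decision that comes slightly later. No patient, visit, sample or dose level changes.

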5.3.1 Rules for Dose Finding

The DLT evaluation period will be a minimum of 1 week (7 days) (see Section 5.3.2.1).

Patients will be randomized (1:1 ratio) in groups of at least 10 patients (5 bempegaldesleukin/SOC and 5 placebo/SOC) in each dose cohort unless unacceptable toxicity is observed.

Unblinding patient treatment assignment, if required, for the purpose of dose-limiting toxicity (DLT) adjudication will be performed in accordance with Nektar Therapeutics internal procedures for unblinding and associated documentation.

The definition of a DLT is provided in Section 5.3.2.1. If no DLTs occur in a cohort of at least 5 patients who received bempegaldesleukin, a new cohort of 10 patients may be randomized and treated at the next higher dose level (Table 8). If only 1 of the 5 patients who received bempegaldesleukin in a dose cohort experiences a CRC-confirmed DLT, then the next cohort of 10 patients may be treated at the next higher dose level. If 2 or more patients who received bempegaldesleukin within a cohort experience CRC-confirmed DLTs, then that dose level will be above the MTD (the highest dose tested where no more than 1 of 5 patients who received bempegaldesleukin has experienced a CRC-confirmed DLT). If 10 patients have already been enrolled into a cohort and additional patients have signed the ICF and are undergoing the screening process, they may be enrolled to the cohort with Sponsor approval; however, these patients are not required to be included in the dose escalation or de-escalation decision for that cohort.

Approximately 30 patients will be enrolled.

5.3.2 **Dose-Limiting Toxicities (DLTs)**

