	Eligible patients will be enrolled into 1 of 3 dose cohorts with doses ranging from 0.00075 mg/kg to 0.003 mg/kg. The first two patients randomized and treated in each dose cohort (1 with bempegaldesleukin/SOC and 1 with placebo/SOC) will serve as sentinel patients. Enrollment in each cohort will be staggered as follows. A Cohort Review Committee (CRC) will monitor blinded safety and tolerability data for the first 72 hours after study drug administration from the 2 sentinel patients before additional patients in that cohort are treated. If the CRC determines additional patients may be randomized, 2 patients will be randomized (1 with bempegaldesleukin/SOC and 1 with placebo/SOC), treated with study drug, and observed for 72 hours. For every 2 patients, the Medical Monitor will review the blinded safety and tolerability data for the first 72 hours after study drug administration to determine if the next 2 patients may be randomized. If it is not possible to assess the protocol-defined DLT criteria (see Section 5.3.2.1.1), the Medical Monitor will request a review of the safety data by the CRC. After 10 patients have completed a 7-day observation period for dose-limiting toxicity (DLT; see Section 5.3.2.1 for additional details), the CRC will assess the accumulated, blinded safety and tolerability data, as well as any available pharmacokinetic, pharmacodynamic, and disease measurement data, to determine whether dose escalation or de-escalation from the tested bempegaldesleukin dose level is warranted. This decision will be based on blinded data using pre-defined criteria, including the proportion of patients who experience a DLT (see Section 5.3.1). Patients who drop out of the study for reasons other than a DLT, before the DLT evaluation period (Days 1 to 7) has elapsed, may be replaced.			

Key Eligibility Criteria:	The following list contains key eligibility criteria only; a full list of eligibility criteria is provided in Section 4.0.
	 Key Inclusion Criteria: Provide written, informed consent to participate in the study and follow the study procedures.
	 Male or female patients, age 18 years or older on the day of signing the informed consent form.
	• Agrees to admission to an in-patient facility for monitoring from Days 1 to 8, inclusiv

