5.3.2.1 Determination of Dose-Limiting Toxicities (DLTs)

The DLT evaluation period will be a minimum of 1 week (7 days) because possible drug-related AEs are most likely to occur 1 to 5 days following bempegaldesleukin treatment based on the following:

- Previous experience with bempegaldesleukin in cancer patients including clinical safety data from 605 patients treated primarily with bempegaldesleukin at higher, oncology dose levels (most often, bempegaldesleukin 0.006 mg/kg) than will be used in this trial (see Section 2.2.4.1).
- The clinical half-life of bempegaldesleukin, which is approximately 20 hours (see Section 2.1.3.1).
- The rate of active species formation from the inactive bempegaldesleukin pro-drug (see Section 2.1.3).
- The chronic nonclinical toxicology studies (see Section 2.2.4.2).

DLTs will be assessed by the CRC during the DLT evaluation period. If DLTs are not observed, dose escalation will be permitted and enrollment of the next dosing cohort may begin. If DLTs are not observed, patients will continue to enroll until no more than 30 patients have been evaluable for safety. Grading of AEs is described in Section 7.3. Patients who drop out of the study for reasons other than a DLT, before the DLT evaluation period has elapsed, may be replaced.

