5.6.2 Treatment of Study Drug-Related Infusion Reactions

Infusion reactions have been reported during infusions with bempegaldesleukin. If such a reaction were to occur with the study drug infusion, it might manifest with fever, chills, rigors, headache, rash, pruritus, arthralgias, hypotension, hypertension, bronchospasm, or other allergic-like reactions. Infusion reactions should be graded as outlined below (consistent with CTCAE version 5.0 grading of infusion-related reaction); please also refer to Section 7.3.

Treatment recommendations are provided below and may be modified based on local treatment standards and guidelines, as appropriate:

- For **Grade 1** symptoms (mild reaction; infusion interruption not indicated; intervention not indicated): Remain at the bedside and monitor the patient until recovery from symptoms.
- For Grade ≥ 2 symptoms: Immediately discontinue study drug infusion and begin an IV infusion of normal saline, and treat the patient with diphenhydramine 50 mg IV (or equivalent) and/or acetaminophen/paracetamol 325 to 1000 mg; remain at the bedside and monitor the patient until resolution of symptoms. Corticosteroid and/or bronchodilator therapy may also be administered as appropriate. Corticosteroid doses should be minimized (eg, ≤ 80 mg/day methylprednisolone) to avoid exacerbating impairment of immune function. Salbutamol may be given as 4 puffs (400 mcg) as the initial dose and increase by 2 puffs every 2 min up to 10 puffs if needed.

• For **Grade 3 or Grade 4** symptoms: immediately discontinue study drug infusion. Begin an IV infusion of normal saline and treat the patient as follows: recommend bronchodilators, epinephrine 0.2 to 1 mg of a 1:1000 solution for subcutaneous administration or 0.1 to 0.25 mg of a 1:10,000 solution injected slowly for IV administration, and/or diphenhydramine 50 mg IV with methylprednisolone 100 mg IV (or equivalent), as needed. Study drug will be permanently discontinued. The patient should be monitored until the Investigator is comfortable that the symptoms will not recur. Investigators should follow their institutional guidelines for the treatment of anaphylaxis. Remain at the bedside and monitor the patient until recovery of the symptoms.

In case of late-occurring hypersensitivity symptoms (eg, appearance of a localized or generalized pruritus within 1 week after treatment), symptomatic treatment may be given (eg, oral antihistamine or corticosteroids).

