9.2 Determination of Sample Size

This Phase 1b study will assess the safety and tolerability of different doses of bempegaldesleukin. No formal sample size calculation is done. Around 10 patients per dose cohort with a 1:1 randomization ratio (5 bempegaldesleukin/SOC and 5 placebo/SOC) to bempegaldesleukin/SOC or placebo/SOC will be enrolled.

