9.3 Analysis Sets

For the purpose of analysis, the following populations are defined:

Population	Description
Safety Population	All patients who receive at least 1 dose (or partial dose) of study drug.
-	All patients in the Safety Population who have evaluable concentration-time profiles that allow for computation of meaningful PK parameter values.

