7.5 Study Treatment Exposure

Total dose administered (mg, mg/kg) will be summarized by N (observed), mean, SD, median, Q1, Q3, min, and max for each bempegaldesleukin dose level in Treated Population. Number and percentage of patients with full dose will be provided for each bempegaldesleukin dose level and total in the Treated Population.

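### The 1-of-5 escalation rule sets no minimum dose received, so a patient whose infusion is stopped short without a DLT can fill one of the five bempegaldesleukin places

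*Protocol*

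**What the plan says.** **The count.** Protocol 5.3.1 allows escalation as follows: "If no DLTs occur in a cohort of at least 5 patients who received bempegaldesleukin, a new cohort of 10 patients may be randomized". One confirmed DLT among the five also allows it; two or more place the dose above the MTD. The MTD is "the highest dose tested where no more than 1 of 5 patients who received bempegaldesleukin has experienced a CRC-confirmed DLT". None of these sentences states how much of the dose a patient must have had.

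**The population.** Neither document defines a DLT-evaluable set. The Protocol 9.3 Safety Population is "All patients who receive at least 1 dose (or partial dose) of study drug", and SAP 6.0 agrees. SAP 11.1 tabulates DLTs on that population.

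**Stopping an infusion.** For reactions of Grade 2 and above, Protocol 5.6.2 says "Immediately discontinue study drug infusion and begin an IV infusion of normal saline". Permanent discontinuation is mentioned only under Grade 3 or 4. In 5.3.2.1.1 a drug-related adverse event becomes a DLT at Grade 3.

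**Replacement.** Protocol 5.3.2.1 says: "Patients who drop out of the study for reasons other than a DLT, before the DLT evaluation period has elapsed, may be replaced". The synopsis, 5.3 and 5.15 repeat this. Under 5.7, a patient taken off study drug for a clinically significant adverse event stays in follow-up, so is not a drop-out on that account. Section 5.15 allows at most ten patients per cohort, five per arm, to complete the DLT period.

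**Exposure.** SAP 7.5 says: "Number and percentage of patients with full dose will be provided for each bempegaldesleukin dose level". Nothing links that tabulation to the DLT count.

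**The concern.** The issue is the amount of drug delivered, not the length of observation. A patient stopped part-way through a single 15-minute infusion can complete all seven days of the DLT period, have no DLT, and so occupy one of five places in the test of a dose that he or she did not receive in full.

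This matters for this drug because Protocol 2.1.4.2.3 places the main risk period at the release of the active moieties, which peak 24 to 48 hours after dosing. A partly dosed patient passes through that window on less than the assigned amount. Protocol 2.1.4.2.4 describes the heart-rate effect as dose-related, and 2.2.4.3 suggests dose-response for several cytokines. If a smaller amount carries a smaller DLT risk, the cohort is a weaker test of the dose than five full doses. What follows from the count is the MTD, possibly the RP2D, and a next cohort at twice the dose (0.0015 / 0.00075 = 2; 0.003 / 0.0015 = 2).

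**Working it through.** **The plan's own figure.** The synopsis says "Eligible patients will be enrolled into 1 of 3 dose cohorts with doses ranging from" 0.00075 to 0.003 mg/kg, and each cohort has ten patients. 3 × 10 = 30, which matches the planned total of about 30. No target DLT rate and no operating characteristic for the 1-of-5 rule is given, so there is nothing further to reproduce.

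**Inputs.** From Protocol 5.3.1 and 9.2: five bempegaldesleukin patients per cohort, and a dose is cleared with at most one confirmed DLT. Assumed, because the documents do not give them:
- p, the true DLT rate at the full dose, from 0.10 to 0.50
- f, the DLT risk of a partly dosed patient relative to a full dose, from 0 (no risk) to 1 (same risk)
- s, the chance that an infusion is stopped and not completed without a DLT

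**Five full doses.** P(clear) = (1−p)^5 + 5p(1−p)^4.
- p = 0.40: 0.0778 + 0.2592 = 0.337
- p = 0.30: 0.1681 + 0.3602 = 0.528

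**Four full doses and one partial dose.** P(clear) = (1−p)^4 + 4p(1−p)^3 × (1−fp).
- p = 0.40, f = 0: 0.1296 + 0.3456 = 0.475
- p = 0.40, f = 0.5: 0.1296 + 0.3456 × 0.8 = 0.406
- p = 0.40, f = 1: 0.1296 + 0.3456 × 0.6 = 0.337
- p = 0.30, f = 0: 0.2401 + 0.4116 = 0.652

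| True DLT rate p | 5 full doses | 1 partial, f = 0.5 | 1 partial, f = 0 |
|---|---|---|---|
| 0.20 | 0.737 | 0.778 | 0.819 |
| 0.30 | 0.528 | 0.590 | 0.652 |
| 0.40 | 0.337 | 0.406 | 0.475 |
| 0.50 | 0.188 | 0.250 | 0.312 |

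At p = 0.10 even the f = 0 case moves only from 0.919 to 0.948. With two partial doses at p = 0.40, the chance is 0.484 at f = 0.5 and 0.648 at f = 0.

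**What a clean cohort shows.** With no DLT, the one-sided 95% upper limit for the DLT rate is 1 − 0.05^(1/n): 0.451 with five full doses and 0.527 with four.

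**Allowing for frequency.** The chance of at least one such stop among five is 1 − (1−s)^5: 0.096, 0.226 and 0.410 for s = 2%, 5% and 10%. Averaged over whether a stop occurs, with f = 0, each patient's DLT risk is p(1−s). At p = 0.40 the chance of clearing is then 0.351, 0.372 and 0.409, against 0.337 with no stops.

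**The case against.** **Inference from wording.** No sentence says that a partly dosed patient counts. The Safety Population and SAP 11.1 govern analysis and reporting, and 5.3.1 does not cite them. A reader might infer that the plan deliberately treats a partial dose as a full, DLT-free one; the documents do not say so. What stands is that the only stated condition is having received the drug, and nothing excludes such a patient.

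**Narrow route.** Section 5.6.2 does not say whether a Grade 2 infusion may resume, and its recommendations may be adapted locally. Confirmed drug-related Grade 3 or 4 reactions in bempegaldesleukin patients are DLTs. So a reader should not infer that every partial dose favours clearing. The point concerns only stops without a DLT that are not completed: a Grade 2 reaction or a technical stop.

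**Visibility and discretion.** A stopped infusion is not hidden. Action taken with study drug is recorded for each adverse event (7.2), and the first 72 hours are reviewed for every pair (5.3). Five patients are not the only safeguard either: escalation is permissive, the Cohort Review Committee weighs all available data, and sentinels and pausing criteria apply. The committee can discount such a patient. But nothing requires it to, and it works on blinded data. Unblinding is provided for when the DLT criteria cannot be assessed, and a Grade 2 stop can be assessed readily as not a DLT. The committee may therefore not know that the patient was one of the five on active drug.

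**Size.** Zero risk in a patient who has just reacted to the drug is an extreme assumption, and 30% to 40% may be high: Tables 4 and 5 show no related Grade 3 to 5 event in 4 + 3 = 7 patients at 0.003 mg/kg. This is fair, though seven is few, and it is why a range is given.

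**Conclusion.** The gap is real and worth closing. As worded, the count and the replacement provision together allow a patient with an incomplete infusion and no DLT to take one of the five places, and provide no replacement.

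Conditional on one such patient and a true DLT rate of 40%, the chance of clearing the dose goes from 34% to between 34% and 48%, with 41% at half the risk. At 30% the upper bound is 65% against 53%. These figures rest on assumed values of p and f, and how often the situation would arise cannot be judged from the documents.

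A reader might go further and conclude that doses will be cleared on patients who did not receive them. The documents do not support that: such a patient received part of the dose, and the committee is free not to escalate.

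**What to change.** In Protocol 5.3.1 and SAP 11.1, define a DLT-evaluable set: bempegaldesleukin patients who received at least a prespecified share of the planned dose, or who had a committee-confirmed DLT after any amount. Make it the denominator of the 1-of-5 rule. The share is for the sponsor to set; SAP 7.5 already identifies full-dose patients.

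In 5.3, 5.3.2.1 and 5.15, extend replacement to patients with an incomplete infusion and no DLT, and keep them in the Safety Population. Four places must be reconciled with this:
- **Ten completers in 5.15.** A retained patient plus one replacement makes 10 + 1 = 11, or 12 if a pair is added. Section 5.3.1 already speaks of cohorts of at least ten.
- **The limit of 30 safety-evaluable patients in 5.3.2.1.**
- **The 1:1 paired stagger.** State whether a replacement is a single patient or a pair. Applying the provision to stopped infusions in either arm avoids disclosing treatment by calling for a replacement.
- **Section 5.6.2.** Its wording on stopping at Grade 2 and at Grade 3 or 4 should make clear when an infusion counts as incomplete.

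The cost is protocol and SAP wording and, occasionally, one extra patient or pair with one further 72-hour hold.
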